13.1 Data and Safety Monitoring Plan	

13.2 Data and Safety Monitoring Board

13.3 Potential Study Benefits

13.4 Alternatives to Participation

13.5 Risk/Benefit Assessment

1. Abstract

Identifying effective strategies for treating obesity is both a clinical challenge and a public health priority. Between 1960 and 2010, obesity prevalence (body mass index [BMI] ≥ 30 kg/m²) in US adults increased from 11% to 35.5% in men and from 16% to 35.8% in women, and about 70% of US adults are considered either overweight or obese. This situation has troubling implications, as obesity in young adulthood and middle age translates into higher rates of cardiovascular risk factors, disability, hospitalization, Medicare expenditures, and mortality risk later in life. While a variety of approaches are successful in achieving initial weight loss techniques for combining initial weight loss and successful maintenance of weight loss have been elusive. Research shows that most people who successfully lose weight will regain 1/3 to 2/3 of that weight after one year. Rigorous testing of promising, innovative approaches to weight loss and maintenance is an important public health priority. While both behavioral economic and environmental strategies have shown promise, we propose to test a novel blend of these approaches in this initiative. We will also test these interventions in populations with a high rate of African Americans and low to moderate income individuals who are obese, addressing important concerns about the health disparities due to high rates of obesity. The proposed study will evaluate the comparative effectiveness of behavioral economic financial incentives and environmental strategies, separately and together, in achieving initial weight loss and maintenance of weight loss, in obese employee populations. Our study contributes to the CDC's efforts to combat obesity but in particular to CDC's winnable battles (physical activity and obesity); the NCCDPHP strategic priorities around well-being, health equity, and evaluation and dissemination of environmental and systems-wide solutions to address public health problems; and the NCCDPHP domain around healthier worksite initiatives, CDC efforts to improve nutrition and physical activity to prevent obesity, and reduction of cardiovascular disease risk. We propose a 4-arm randomized controlled trial (RCT) in which 344 employees of the City of Philadelphia, IBC, and SEPTA with initial Body Mass Index of 30 or greater and at least 1 other cardiovascular risk factor (high blood pressure, hypercholesterolemia, diabetes, smoking) will be randomized to receive one of the following: 1) Daily lottery type incentives tied to achievement of weight loss goals (incentive arm); 2) individually tailored environmental strategies around food intake and physical activity (environmental arm); 3) a combination of incentives and environmental strategies (combined arm); or 4) standard employee wellness benefits and weigh-ins every 6 months (control arm). Phase I of the study (first 6 months) will focus on weight loss; Phase II (months 7-18) will focus on continued weight loss or maintenance for those who choose to maintain weight loss as opposed to

continuing to try to lose weight; Phase III (months 19-24) will provide a period of post-intervention follow-up to measure sustainability of effects.

2. Background

2.1 Impact of Obesity on Health, Benefits of Weight Loss. Obesity is the second leading cause of preventable death in the United States, associated with high blood pressure (BP), type 2 diabetes, coronary heart disease, and osteoarthritis. Weight loss of just 5-10 kg can improve risk factors (e.g., BP, glycemia, and serum lipid levels) and reduce the incidence of diabetes. In older adults, weight loss interventions have shown clear improvements in BP, arthritis, and functional status. However, maintenance of weight loss is needed to achieve long term health benefits, and successful strategies for long-term maintenance are lacking. Weight regain after a period of intentional weight loss is widely observed with all interventions due to loss of motivation, lack of sustained rewards for weight loss behavior, difficulty adhering to diet, and need for ego-depleting exertion of willpower. Since weight loss programs offered as part of standard employer-sponsored benefits are generally unsuccessful in achieving weight loss maintenance, supplemental motivation from incentives or environmental feedback may help people keep weight off.

2.2 Changes in benefit design and the use of incentives for employees. There have been significant shifts in recent years in the use of incentives to increase healthy behaviors among employees of American companies. HIPAA's 2006 regulations permitted employer health plans to offer financial incentives for achieving health- contingent standards such as body mass index as long as this was part of a wellness program. Programs were required to meet a number of conditions, including that they have a "reasonable chance" of improving health and not be "overly burdensome. The Affordable Care Act (ACA) increased the incentive ceiling to 30% of coverage costs and gave regulators the authority to further increase the ceiling to 50% if "appropriate." In recently issued final rules, regulators lifted the ceiling to 50% as long as any incentives beyond the 30% threshold targeted tobacco use.⁹⁹ In 2013, approximately 85% of large employers in the US are using incentives for healthy behavior, making the use of such approaches increasingly a widely used standard for efforts to reduce obesity. However, the approaches being utilized generally have not been well tested and rarely utilize insights from behavioral economics that utilize the decision errors that are common in people to design more effective programs. These strategies also fail to incorporate environmental change strategies which are increasingly recognized as important to obesity reduction and maintenance of healthy weight, and few such strategies have been rigorously evaluated in the context of weight management programs.

2.3 Use of Financial Incentives to Change Health Behaviors in General. Individuals put disproportionate value on present relative to future costs and benefits, known as present-biased preferences. While this bias typically works against healthy behavior, the same factors can be used to promote healthy behavior by providing tangible but small immediate rewards for beneficial behaviors. Evidence from hard-to-change behaviors such as tobacco and other substance use, indicate that incentives can be beneficial, but patients require regular monitoring, and frequent feedback is an important component to success. A review of 11 randomized trials of financial incentives found that financial incentives promoted adherence better than any tested alternative, leading to better blood pressure control, appointment

attendance, and higher immunization rates. Other reviews have found various incentives (including lotteries) effective in changing behavior. However, few studies have examined longer-term effects of incentives on health behaviors after cessation of incentives, or the relative effectiveness of incentives vs. other obesity reduction strategies. Lottery-type incentives are particularly appealing for improving adherence to a weight loss regimen. Although small payouts (e.g., \$10 to quit smoking) may not be effective, lottery incentives have shown promise in altering health behaviors even when awards have relatively low expected values (e.g., \$50). Lotteries typically include several features that make them so appealing, despite a very low rate of return. They typically offer a combination of a relatively large chance of a small payout and a very small chance of a larger payout. The frequent small payoffs increase the attractiveness of lotteries by giving lottery players intermittent positive reinforcement. Moreover, the feedback is often very rapid; most games have daily draws and more than 40% of state revenues now come from instant scratch-off tickets. The small chance of a large payoff is especially attractive because people tend to overweigh small probabilities in making decisions. Structuring financial incentives as a lottery has several benefits over a set pay-off amount. Lotteries may be less costly to provide than comparable cash incentives because of the effectiveness of intermittent reinforcement. Beyond their monetary payoffs, lotteries provide entertainment value, enhancing their reinforcing properties as a motivator. Lotteries may be particularly effective in lower-income populations (in whom lotteries are more popular), who have higher rates of non-adherence than other populations.

2.4 Effects of Financial Incentive Interventions for Obese Patients. Incentives are effective in weight loss interventions. Jeffery et al showed that participants without any weight management training lost weight when they deposited valuables with a therapist with return of their valuables contingent on progress towards pre-specified goals, and that incentives for weight loss are more effective than incentives for attending weight loss training. Finkelstein et al. found that over a 3- month period, participants offered \$14 per percentage point of weight loss lost 4.7 pounds whereas participants offered \$7 lost 3.0 pounds and control participants lost 2.0 pounds. In work done by our group using daily lotteries (published in JAMA), we found that about 50% of participants offered an incentive reached a weight loss goal of 1 pound per week over 16 weeks (average weight loss 13.1 pounds) compared to about 10% of control group participants (average weight loss 4.0 pounds). Dropout rates were about 7%, remarkably low for a weight loss intervention. Further work extended successful weight loss to 8 months and showed the effectiveness of competition between groups in augmenting motivation, though the individual arm was less effective without frequent feedback. These studies illustrate that incentives ideally provide frequent feedback, and that daily lottery incentives using a technology platform can be highly effective at sustaining engagement and achievement of weight loss goals.

2.5 Impact of Environmental Changes on Food intake and Physical activity. It has long been recognized that social and physical environmental factors influence food intake and physical activity. Worksite interventions to improve food environments have shown modest success. Most worksite nutrition and weight intervention studies have not included clearly defined environmental strategies, though combination interventions have achieved significant, albeit modest, success. The use of environmental interventions to increase physical activity is recommended, though the evidence base of intervention

research is limited. Cross-sectional research indicates that having multiple environmental supports (stairways, facilities, equipment) at worksites is associated with meeting physical activity interventions. In addition to environmental changes to worksite structures, environmental re-engineering is a promising strategy and is being studied in several trials with a home environment focus. A recent study of environmental changes for weight gain prevention in worksites found no impact on body mass from environmental changes alone, perhaps due to limited strength of the interventions, deployment of single strategies in isolation, inadequate implementation, and because such studies included normal weight, overweight, and obese employees.

2.6 Cost of Obesity and Cost-effectiveness of Behavioral Interventions. Recent studies concluded that annual US expenditures attributable to overweight and obesity are between \$90 and \$100 billion. Among nationally representative cohorts, the average annual incremental cost of obesity is about \$1,308. Higher BMIs in young adulthood and middle age are associated with substantially higher Medicare expenditures in old age. Higher BMI also translates into significantly higher health care charges within 18 months, suggesting that health plans may find it cost effective to invest in behavior modification to lower health expenditures. Several economic assessments of behavioral interventions for weight loss have been published. The Diabetes Prevention Program, reported that, compared to placebo, the intensive lifestyle intervention had cost per QALY ratios ranging between \$32,000 and \$52,000, depending upon whether direct medical costs alone or direct and indirect costs were counted. Finkelstein et al. reported that the 1-year incremental cost per 1% reduction in 10-year CHD risk associated with an enhanced behavioral intervention was \$637.135. The substantial health and economic consequences of obesity highlight the importance of testing new approaches to maintenance of weight loss and the potential cost effectiveness of successful interventions.

3. Data Management and the Way to Health Platform

The Way to Health online platform will serve as the core mechanism for recruiting and enrolling subjects, transmitting general and intervention-specific messages, collecting individual weight measurements and online survey data, and providing regular feedback to subjects on their progress in the study. This platform has supported a series of other NIH-funded studies that harness new technologies to encourage healthy behaviors and treatment adherence. The University of Pennsylvania Biomedical Informatics Consortium (BMIC) will be the hub for the hardware and database infrastructure that will support the project and where the web portal is based. The data collected for this study will be stored in MySQL databases on a dedicated BMIC-run server. All data will be stored in both a non-editable database and in a separate modifiable database, allowing researchers to correct mistakes while preserving the raw data for auditing purposes. Every SQL transaction, including accessing and changing data, will be logged for auditing purposes. Data will be entered into the database through several different mechanisms. Participants will enter their own personal information and respond to surveys through a PHP-based web interface. Researchers will have a separate interface that will allow them to manually enter data if needed. The dataset will be blinded of all personally identifiable information when exported for analysis. The web application will automatically remove all identifiers when a researcher requests an analytic dataset. The only people with access to identifiable participant information will be pre-specified research staff responsible for contacting participants for

follow-up. Personal information and research data will be stored in separate SQL tables and will be linked by a computer-generated ID number. Furthermore, the web platform will be set up with pre-specified ranges of eligible values for most questions to minimize participants' data entry errors. Specifically designated administrators will have the ability to make corrections. Each modification, however, will be logged along with justification for the change. The original data will be preserved in a separate non-modifiable database. The UPENN Biomedical Informatics Consortium (BMIC) will be the hub for the hardware and database infrastructure that will support the project and where the Way to Health web portal is based. The BMIC is a joint effort of the University of Pennsylvania's Abramson Cancer Center, the Cardiovascular Institute, the Department of Pathology, and the Leonard Davis Institute. The BMIC provides a secure computing environment for a large volume of highly sensitive data, including clinical, genetic, socioeconomic, and financial information. Among the IT projects currently managed by BMIC are: (1) the capture and organization of complex, longitudinal clinical data via web and clinical applications portals from cancer patients enrolled in clinical trials; (2) the integration of genetic array databases and clinical data obtained from patients with cardiovascular disease; (3) computational biology and cytometry database management and analyses; (4) economic and health policy research using Medicare claims from over 40 million Medicare beneficiaries. BMIC requires all users of data or applications on BMIC servers to complete a BMIC-hosted cybersecurity awareness course annually, which stresses federal data security policies under data use agreements with the university. Curriculum includes HIPAA training and covers secure data transfer, passwords, computer security habits and knowledge of what constitutes misuse or inappropriate use of the server. We will implement multiple, redundant protective measures to guarantee the privacy and security of the participant data. All investigators and research staff with direct access to the identifiable data will be required to undergo annual responsible conduct of research, cybersecurity, and Health Insurance Portability and Accountability Act certification in accordance with University of Pennsylvania regulations. All data for this project will be stored on the secure/firewalled servers of the BMIC Data Center, in data files that will be protected by multiple password layers. These data servers are maintained in a guarded facility behind several locked doors, with very limited physical access rights. They are also cyber-protected by extensive firewalls and multiple layers of communication encryption. Electronic access rights are carefully controlled by University of Pennsylvania system managers. We will use highly secure methods of data encryption for all transactions involving participants' financial information using a level of security comparable to what is used in commercial financial transactions. We believe this multi-layer system of data security, identical to the system protecting the University of Pennsylvania Health Systems medical records, greatly minimizes the risk of loss of privacy.

4. Overall Objectives/Specific Aims

Primary

1. Assess the effectiveness of a daily lottery-based financial incentive, relative to the control group, on cumulative weight loss over an 18-month period. *H1: Mean weight loss from baseline to 18 months among participants randomized to the lottery incentive will be at least 5 kg greater than among control group participants.*

2. Assess the effectiveness of environmental strategies, relative to the control group, on cumulative weight loss over an 18-month period. *H2: Mean weight loss from baseline to 18 months among participants randomized to the environmental strategies group will be at least 5 kg greater than among control group participants.*
3. Assess the effectiveness of the combined incentives and environmental strategies arm, relative to the control group, on cumulative weight loss over an 18-month period. *H3: Mean weight loss from baseline to 18 months among participants randomized to the combined arm will be at least 8 kg greater than among control group participants.*
4. Assess the comparative effectiveness of a combination of lottery-based financial incentives and environmental strategies on cumulative weight loss over an 18-month period. *H4: Mean weight loss among participants randomized to the combined arm will be at least 3 kg greater than among participants in either of the individual arms.*

Secondary

5. Assess costs of each of the intervention arms from both the employer and social perspective and compare cost differences between each arm relative to effectiveness measured by incremental weight loss achieved. *H5: From an employer's perspective, each individual intervention will have favorable cost-effectiveness ratios relative to control; the combined arm will have a favorable cost-effectiveness ratio relative to individual arms.*

5. Primary Outcome Variable

5.1 Change in weight from baseline to 18 months.

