All hypotheses will be tested using two-sided, 0.05-level tests unless otherwise specified (notably the Holm testing approach will be used for the five primary hypotheses in Specific Aims 1-4). The primary analyses will be an unadjusted intent-to-treat analyses, using a t-test for differences in weight change from baseline to 18 months, as measured by the in-person weight, between each intervention group and the control group, and the combined compared to each single intervention, applying the Holm p-value correction for multiple comparisons testing. If weight change appears to be non-normally distributed in the blinded data, we will find an appropriate. Missing data will be handled as described above.

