Weight change between baseline and 18 months, with 95% confidence intervals (CIs), will be estimated for comparison with adjusted analyses. We will estimate regression models adjusted for the stratification variables (sex, employer, initial BMI) and other participant characteristics factors including age, race, income, and education. We will evaluate the evidence of confounding for other baseline variables (baseline weight, marital status, household size, physical activities- i.e total minutes of MVPA+walking/week, eating behavior index, stages of change, SF-36 General Health) using change in estimate criterion (10%). We will fit exploratory models of the repeated weight measurements that incorporate time as a polynomial function or using visit-specific indicator variables to determine the most parsimonious model that adequately describes the observed patterns, as necessary. Models will be built separately for the in-person and at home weight data. Models using the at-home weight data would be considered only as potential exploratory analyses comparing the 3 intervention arms, since at-home weights are not available for the control arm. We will investigate random-effects models that allow for baseline individual variability as well as variability in the changes in weights over time; an example is the following: $E(\text{weight}_{ij}) = \beta_0 + \beta_1 \text{Time}_j + \beta_2 \text{Group}_i + \beta_3 X_i + b_{0i} + b_{1i} \text{Time}_j$, where i indicates subject, j indicates assessment times, the parameters are fixed effects linking time, a treatment group vector, and a vector of other demographic or clinical covariates X_i to the outcomes, and b_{0i} and b_{1i} are random intercept and slope effects. Tests for significance of random effects will use likelihood ratio tests for nested models; we will compare models with different random effects structures using the maximized log-likelihoods and the Akaike Information Criterion (AIC). We will apply standard diagnostic techniques to assess model adequacy. We will use treatment by time interactions to assess whether the rate of change in weight differs by intervention arm. We hypothesize that incentives may be more effective among lower income individuals and will evaluate this using interaction terms of income with treatment group. We will explore differential effects by race and education and baseline levels of intrinsic motivation and stages of change. We will also consider other potential mediators, such as the home food and activity environment. To assess the sensitivity of treatment effect estimates to missing

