11.2 Power and Sample Size Considerations

We have designed the study with adequate power to detect differences in weight loss over an 18-month period. Our intervention should achieve its maximal impact in maintaining initial weight loss at the end of Phase II (month 18), when the incentive payments cease. To maintain the experiment-wide Type I error and guard against false conclusions of effectiveness, we will use the Holm multiple comparisons adjustment for test the 5 primary comparisons in Specific Aims 1-4 . If the interventions are as effective as hypothesized, the proposed sample size maintains greater than 90% power to show significance for each of the three intervention arms compared to control and greater than 80% power to show significance for the combined intervention group compared to each of the two interventions alone.

It is important to note that while we originally planned to recruit 328 participants, a small subset was unable to successfully set up their Withings scales post randomization due to Wi-Fi connectivity issues. Therefore, we increased our target sample size by the number of people who were unable to connect their Withings scales to the Way To Health platform (16 additional subjects), bringing our recruitment total to 344 participants. The final statistical analysis is adjusted for the stratification factors to account for any imbalances that may have occurred. We have previously communicated this information to the IRB and the members of the Data Safety and Monitoring Board (DSMB), who approved this approach. The following information outlines our original power calculations and sample size considerations.

We plan to recruit approximately one third of the participants required for the start of Phase I from each of our participating employers (IBC, SEPTA, and City of Philadelphia). Given the large number of potentially eligible employees, we can, if needed, easily increase the proportion of participants from any of these employers to meet recruitment targets. Participants will be randomized to our 3 intervention groups and the control group using a 1:1 ratio for the intervention arms. We built in a margin of 20% of

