our original target sample size of 328 for potential attrition before the 18-month assessment, resulting in an expected 260 participants (65 per arm) who are available for analysis at the end of Phase II. This sample size will provide us with greater than 90% power to detect a difference in weight change between baseline and the 18-month weigh-in of 5 kg between each single intervention group and the control group (primary outcomes for Specific Aims 1-3) and 87% power to detect a 3 kg difference between the combined group and either the incentive or environmental strategies groups (Specific Aim 4). Namely, we will have greater than 85% power for the 5 primary comparisons of interest for an expected weight change between months 0-18 of -8 kg, -5 kg and 0 kg in the combined, intervention and control groups, respectively (a net difference between single intervention and control groups of 5 kg, combined intervention and control groups of 8 kg, and 3kg between the single interventions and combined group) and assuming a standard deviation (S.D.) of weight loss of 5 kg. We will also have greater than 80% power to detect a difference of 4.6 kg in weight change between single intervention and control groups and 7.3 kg between the combined and control groups (primary outcomes for Specific Aims 1-3), while maintaining approximately 80% power for a 2.7 kg difference between the combined and each single intervention (Specific Aim 4). For our secondary outcomes (Specific Aim 5), we wish to compare the cost differences between each arm relative to the effectiveness measured by incremental weight loss achieved. We will calculate a point estimate of cost per kg of weight loss based on estimated inter-arm differences in weight loss and the incremental cost of the interventions, as described in C.3.d.ii.c. For weight loss at 18 months, given an expected incremental cost of \$810 (incentives) and incremental weight loss of 5 kg, 328 participants provide 80% power to detect a cost per kg lost of \$430 and greater than 90% power to detect a cost per kg lost of \$575. This study is primarily a test of the efficacy of these interventions. Due to resource constraints and because we do not yet know about intervention effectiveness, we did not power this study based on cost effectiveness analyses. Estimated detectable costs per kg are a function of wide confidence intervals due to sample size.

11.3 Measurement of effect:

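### Do the 'at least' 5, 5, 8 and 3 kg hypotheses in section 4 need rewording to match the t-tests against zero?

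*Combined protocol and SAP*

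**What the plan says.** Section 4 pairs each aim with a hypothesis. The aims carry no threshold: they set out to assess effectiveness against control (Aims 1-3) or the comparative effectiveness of the combination (Aim 4). The thresholds appear only in the hypotheses:

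- H1: mean loss among "participants randomized to the lottery incentive will be at least 5 kg greater than among control group participants".
- H2: mean loss in the "environmental strategies group will be at least 5 kg greater than among control group participants".
- H3: mean loss among "participants randomized to the combined arm will be at least 8 kg greater than among control group participants".
- H4: the same form, with a 3 kg minimum for the combined arm over either single arm.

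Section 11.1 (Efficacy Analyses) says that "the Holm testing approach will be used for the five primary hypotheses in Specific Aims 1-4". The tests are t-tests on the difference in 18-month weight change, two-sided at 0.05 overall. No non-zero null value is given. On estimation, the same section says: "Weight change between baseline and 18 months, with 95% confidence intervals (CIs), will be estimated for comparison with adjusted analyses".

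Section 11.2 introduces its power statement with the condition "If the interventions are as effective as hypothesized". It derives the 5, 8 and 3 kg differences from expected changes of 0, -5 and -8 kg, as section 5.2 also does. It then adds power for smaller effects, including "greater than 80% power to detect a difference of 4.6 kg in weight change between single intervention and control groups".

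**The concern.** Read literally, H1-H4 are claims about minimum effects, and a test against zero cannot confirm such a claim. Section 11.1 names these hypotheses as the family to be tested, so the mismatch appears to reach the primary analysis. A lottery-versus-control difference of, say, 3 kg would be significant but short of H1, and the plan does not say how that would be described. It could be called support for H1 or failure of H1 after the data are seen.

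The interval sentence in section 11.1 refers to weight change without saying whether it means within each arm or between arms. The quantity from which effect size would be judged is therefore not spelled out either.

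**Working it through.** **Inputs.** 65 analysable per arm (260 in all), SD 5 kg, and differences of 5, 5, 8, 3 and 3 kg (sections 5.2 and 11.2). Two-sided 0.05 with Holm over five comparisons (section 11.1). Attrition 20% from the original target of 328: 65/0.80 = 81.25, rounded up to 82, and 4 × 82 = 328.

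**Standard error.** SE = 5 × √(2/65) = 0.877 kg, with 128 degrees of freedom.

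**Reproducing the stated power, with a null of zero (noncentral t).**

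| True difference | Alpha | Computed | Section 11.2 states |
|---|---|---|---|
| 3 kg | 0.025 (two tests left) | 87.4% | 87% |
| 5 kg | 0.01 (first Holm step) | 99.9% | above 90% |
| 2.7 kg | 0.025 | 79.0% (79.9% by the normal formula) | about 80% |
| 4.6 kg | 0.01 | 99.5% | above 80% |

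A simulation of the full five-test Holm procedure at true changes of 0, -5, -5 and -8 kg (100,000 runs) rejects all five in 86.8% of runs. Each 3 kg comparison is rejected in 91%.

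**What a literal reading would imply.** Suppose the null were a difference at or below 5, 8 or 3 kg and the planning effects were exactly true.

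- The chance of showing that a given threshold is exceeded is 2.5% unadjusted, and about 0.5% in the Holm simulation.
- The observed difference reaches its threshold about half the time.
- For 80% power without adjustment, the true difference would have to exceed the threshold by (1.960 + 0.842) × 0.877 = 2.46 kg, that is about 7.5, 10.5 and 5.5 kg.

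None of this fits the stated 87% and above 90%. The power figures agree only with a null of zero.

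**Results that are significant but below the worded value.** The smallest significant observed difference is the critical t times SE: 2.29 kg at alpha 0.01, 1.99 kg at 0.025 and 1.74 kg at 0.05. For H1 and H2 the band from about 2.3 to 5 kg is therefore significant at any Holm step yet below 5 kg. The 95% half-width is 1.979 × 0.877 = 1.74 kg, which gives:

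- observed 4.6 kg: interval 2.9 to 6.3 kg, p < 0.0001;
- observed 2.7 kg: interval 1.0 to 4.4 kg, p = 0.0025.

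In both cases the interval itself shows that the planning value (5 or 3 kg) is neither confirmed nor excluded.

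**Reading the interval sentence in context.** It directly follows the paragraph on between-arm t-tests. Its stated purpose is comparison with adjusted analyses, and the next sentences describe regression models and a 10% change-in-estimate criterion. Those are adjustments to a treatment difference, so between-arm intervals are the natural reading.

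**The case for a change.** The best case for a change is that these are labelled primary hypotheses, that section 11.1 makes them the tested family, and that the fix costs only a few sentences. A result in the band is also plausible. Section 2.4 reports that in the group's previous daily-lottery study the incentive and control results were "over 16 weeks (average weight loss 13.1 pounds) compared to about 10% of control group participants (average weight loss 4.0 pounds"). The net difference is 13.1 - 4.0 = 9.1 lb, or 9.1 × 0.4536 = 4.13 kg, which is below 5 kg. Observed here it would give t = 4.71 and an interval of 2.4 to 5.9 kg.

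Part of this stands. The wording of section 4 does not match the tests, and a reader who sees section 4 alone could take 5 kg for a margin. The example carries little weight, however. That study ran 16 weeks with a goal of 1 lb per week, while this one runs 18 months with 0.5 lb per week in Phase I, and the calculation puts this trial's planning SD on the other study's difference.

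Rewriting H1-H4 would gain little. Without a rule for judging size, a superiority wording leaves the description of a 3 or 4 kg result to the same interval that the plan already provides. Section 11.2 also shows that participants had been randomized when the target was raised from 328 to 344, and softening the primary hypotheses at that stage has a transparency cost of its own.

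**Conclusion.** No change follows. The 5, 5, 8 and 3 kg in H1-H4 are the anticipated effects used for power, phrased as predictions. The aims, the tests and the power statements all treat them that way, and no section makes them a criterion for success. An analyst who follows the plan tests five differences against zero with Holm and reports estimates with 95% intervals, and those results are sound. The sample size, alpha and the stated 87% and above 90% power are unaffected.

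What remains is wording that a careful report settles by giving each between-arm difference with its interval (about ±1.74 kg under the planning assumptions). The report should also say that ordinary 95% intervals are not multiplicity-adjusted and so need not match the Holm decisions: an observed difference between 1.74 and 2.29 kg can exclude zero and still fail Holm.

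This conclusion rests on two inferences. The null of zero is not written out; it is taken from the standard t-test and from the power reproducing only on that basis. The between-arm reading of the interval sentence is taken from its context. The numerical sizes assume 65 analysable per arm and an SD of 5 kg.
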